### 17.2 Physical Examination

Physical examination will be summarized by visit. The following information will be reported (see **Section 8.1** Statistical Tests and Confidence Intervals for a description of summaries to be reported):

- General Appearance (normal, abnormal, not done)
- Respiratory (normal, abnormal, not done)
- Cardiovascular (normal, abnormal, not done)
- Abdomen (normal, abnormal, not done)
- Skin (normal, abnormal, not done)
- Head and Neck (normal, abnormal, not done)
- Lymph Nodes (normal, abnormal, not done)
- Thyroid (normal, abnormal, not done)
- Musculoskeletal (normal, abnormal, not done)
- Neurological symptoms (normal, abnormal, not done)

### 17.3 Vital Signs

Vital signs will be summarized among adult patients ( $\geq$  18 years at informed consent) by visit. The following vital signs measurements will be reported (see **Section 8.1** Statistical Summaries, Tests and Confidence Intervals for a description of statistics to be reported):

- Height (cm)
- Weight (kg)
- Body mass index (BMI) (kg/m^2)
- Temperature (C)
- Heart Rate (beats/min)
- Systolic Blood Pressure (mmHg)
- Diastolic Blood Pressure (mmHg)

Document: Statistical Analysis Plan: AEGR-734-401: A 36-Month, Multicenter, Open Label Phase 4 Study to Evaluate the

Immunogenicity of Daily SC Metreleptin Treatment in Patients with Generalized Lipodystrophy

Author: [name], [name], [name], [name] Version Number: 2.1

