Study Population	Patients who have been prescribed metreleptin for treatment of these conditions will be enrolled in the study, prior to initiation of metreleptin treatment. Pediatric patients will be included since patients with congenital generalized lipodystrophy present with this condition at birth and patients with acquired generalized lipodystrophy often present during early childhood. Assessment of antibodies is required; thus, only patients who have not been previously treatment with metreleptin will be		

Confidential Page 11 of 60

	enrolled in order to document the development of antibodies	
	over time.	
Methodology/Study	MYALEPT [™] (metreleptin) has been approved as an adjunct to	
Design:	diet as replacement therapy to treat the complications of leptin deficiency in patients with congenital or acquired generalized lipodystrophy (MYALEPT Prescribing Information). This study is a multicenter, open-label, Phase 4 trial to provide an assessment of the immunogenicity associated with metreleptin and of any major potential risks due to development of antibodies to metreleptin. The study is being conducted to comply with the postmarketing requirement.	
	Patients who have been prescribed metreleptin for lipodystrophy, who meet all enrollment criteria and sign informed consent for this study at Screening (Visit 1) will receive the first dose of metreleptin at Enrollment/Baseline (Visit 2) at the study site. Patients will return to the study site for follow-up and collection of blood samples at regular intervals (at Months 1, 2, 4, 6, 9, 12, 18, 24, 30, and 36), for a total of 12 visits over 3 years (36 months). All patients with suspected loss of metreleptin efficacy (worsening of metabolic control) or endogenous leptin action (severe infections or sepsis) should be tested for in vitro	
Planned Number of Patients:	neutralizing activity. Ten patients who have been prescribed metreleptin will be enrolled.	
Study Population/ Inclusion Criteria:	For inclusion in the study, patients should fulfill the following criteria at the screening visit:	

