3.3 Safety Objectives

Safety Objectives: Outcome Measure:

Evaluate the safety and tolerability in relation to the development of or absence of anti-metreleptin or anti-huL antibodies, and/or *in vitro* neutralizing activity to metreleptin in patients with congenital or acquired generalized lipodystrophy.

Measure in vitro neutralizing activity in all

Measure *in vitro* neutralizing activity in all patients with suspected loss of response (worsening of metabolic control) or endogenous leptin action (severe infections or sepsis) at time of adverse event report.

SAEs, adverse events leading to discontinuation, loss of response (as assessed by HbA1c and serum triglycerides), severe infections and/or sepsis, standard laboratory tests, and vital signs over time.

Receptor-binding assay titer, cell-based assay category.

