4.3 Inclusion Criteria

For inclusion in the study, patients should fulfill the following criteria at the screening visit:

- 1. Provision of informed consent prior to any study specific procedures. If <18 years of age, has a parent or guardian able to read, understand, and sign the Informed Consent Form (ICF) and a Child Assent form, communicate with the Investigator, and understand and comply with protocol requirements. Adolescent patients must also read and understand the Child Assent Form. If the child is too young or unable to read, then the Child Assent form must be explained to the child.
- 2. Female and/or male patients ≥ 1 years of age.
- 3. Physician-confirmed diagnosis of congenital or acquired generalized lipodystrophy and will begin treatment with MYALEPT for the first time.
- 4. Negative pregnancy test (urine or serum) for female patients of childbearing potential.
- 5. Female patients of childbearing potential must be 1 year postmenopausal, surgically sterile, or be willing to use an acceptable method of contraception (an acceptable method of contraception is defined as a barrier method in conjunction with a spermicide) for the duration of the study (from the time they sign consent). In addition, oral contraceptives, approved contraceptive implant, long-term injectable contraception, intrauterine device, or tubal ligation are allowed. Oral contraception alone is not acceptable; additional barrier methods in conjunction with spermicide must be used.
- 6. Male patients must be surgically sterile or be willing to use an acceptable method of contraception (defined as barrier methods in conjunction with spermicides) for the duration of the study (from the time they sign consent).
- 7. Patients who are blood donors should not donate blood during the study and for 3 months following their last dose of metreleptin.

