7.2.3 Vital Signs

Vital sign measurements will include sitting systolic and diastolic blood pressure and heart rate and body temperature. Vital signs and sitting blood pressure and pulse rate should be measured after the patient rests for approximately 5 minutes and with the patient in a sitting position. The blood pressure measurement should be repeated after at least 30 seconds and the average of the 2 readings recorded.

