10.3 Definitions of Analysis Sets

The following will be used for all analyses:

- Patients treated with at least one dose of metreleptin will be included in the assessment of safety and tolerability.
- Patients treated with a dose of metreleptin and with baseline and postdose efficacy data will be included in the assessment of immunogenicity and efficacy analyses.

Confidential Page 46 of 58

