10.4 Outcome Measures for Analyses

Anti-metreleptin, anti-HuL percent inhibition and binding antibody titers, and category of *in vitro* neutralizing activity to metreleptin in the cell-based assay will be used to assess immunogenicity. Antibody samples will be tested for *in vitro* neutralizing activity using the newly developed receptor-binding assay for metreleptin and cell-based assay methods

HbA1c and fasting triglycerides will be used to assess efficacy.

Serious adverse events, AESIs, AEs leading to discontinuation, vital signs, clinical chemistry, hematology, and urinalysis data will be used to assess safety and tolerability.

The following outcome will be measured:

- Maximum of antibody titer (anti-metreleptin, anti-HuL) by visit
- Percent inhibition of metreleptin and leptin by visit

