10.5 Methods for Statistical Analyses

There will be no hypothesis testing. All data will be summarized by descriptive statistics and/or listings. In general, continuous variables will be summarized by n, mean, SD, median, min and max. Number of patients and percentage of patients in a category will be provided.

Descriptive statistics will be provided for immunogenicity variables (Section 10.4). The maximum antibody titer (anti-metreleptin or anti-HuL) during a visit will be summarized by visit. Categorization of *in vitro* neutralizing activity as assessed by cell-based assay will be summarized across visits; the rate of Category D and E *in vitro* neutralizing activity with 90% and 80% exact confidence intervals will be computed. The results are reported as percent inhibition and 80% inhibition is currently utilized as the neutralizing antibody threshold. activity Results for *in vitro* neutralizing activity will be summarized across visits; however, there will be no formal comparison of the 2 assay methods for the detection and relative potency of Category D or E *in vitro* neutralizing activity.

Maximum antibody titers, neutralizing activities detected by both methods, and metreleptin exposure for each patient will be plotted over time. Maximum antibody

Confidential Page 47 of 58

titers, neutralizing activities detected by both methods, and any associated clinical events (i.e., loss of efficacy or AE) will be summarized.

All AEs will be coded using the Medical Dictionary for Regulatory Activities (MedDRA). The number and percentage of patients who experienced at least 1 AE will be summarized by system organ class and preferred term. AEs will be summarized by relationship to the study medication and by severity. Deaths, SAEs, AESIs, and AEs leading to discontinuation will be tabulated and/or listed. SAEs, AESIs and AEs leading to discontinuation will be summarized respectively by peak antibody titers (antimetreleptin, anti-HuL) and by *in vitro* neutralizing activity categories or percent inhibition.

Clinical laboratory results (hematology, chemistry, and urinalysis), and vital signs results will be summarized using descriptive statistics for each visit.

Change from baseline in HbA1c and percent change from baseline in fasting triglycerides will be summarized for each visit by overall patient population, by peak antibody titers (anti-metreleptin, anti HuL), and by *in vitro* neutralizing activity categories or percent inhibition , respectively.

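### SAP 17.3 limits the by-visit vital-signs summary to adults, although the protocol enrols children from age 1, sets no age limit on that summary, and SAP 4.3 declares no change

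*SAP*

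**What the plan says.** **Protocol.** Section 3.3 names vital signs among the safety outcome measures: "standard laboratory tests, and vital signs over time". Section 10.3 defines who is assessed: "Patients treated with at least one dose of metreleptin will be included in the assessment of safety and tolerability". Section 10.4 says which data serve that assessment: "vital signs, clinical chemistry, hematology, and urinalysis data will be used to assess safety and tolerability". Section 10.5 gives the analysis: "vital signs results will be summarized using descriptive statistics for each visit". None of these sections sets an age limit. Section 7.2.3 defines the measurements: "Vital sign measurements will include sitting systolic and diastolic blood pressure and heart rate and body temperature". Children are an intended part of the population. The synopsis says: "Pediatric patients will be included since patients with congenital generalized lipodystrophy present with this condition at birth", and inclusion criterion 2 in section 4.3 reads: "Female and/or male patients ≥ 1 years of age".

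**SAP.** Section 17.3 says: "Vital signs will be summarized among adult patients", with adulthood fixed as 18 years or more at informed consent. It lists height, weight, BMI, temperature, heart rate and systolic and diastolic blood pressure. Section 17 bases all safety outputs on the safety analysis set (SAF), which section 6.2 defines as all enrolled and dosed subjects. Sections 17.2 (physical examination) and 17.4 (laboratory) have no age limit. Section 4.3 states that nothing in the analysis has changed from the protocol. Section 2 gives the SAP precedence where the two differ.

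**The concern.** The SAP narrows the population for a named safety outcome, gives no reason, and reports in 4.3 that nothing has changed. Because section 2 gives the SAP precedence, the adult-only rule would govern the output, and a reader relying on 4.3 would not know that children had been left out.

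At stake is the descriptive by-visit record of blood pressure, heart rate and temperature in treated children, in a study of 10 or 11 patients that set out to include them. Section 17.3 is also where the SAP summarizes weight and height. Protocol 9.2 names excessive weight loss, particularly in pediatric patients, as a treatment consideration, so children's weight over time is something readers would look for. Age is fixed at consent, so a patient who consents at 17 and turns 18 during the 36 months stays out of the table throughout.

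**Working it through.** The finding rests on comparing the texts. The arithmetic only gives scale.

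**Step 1: the two documents side by side**

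| Question | Protocol | SAP |
|---|---|---|
| Who is in the safety assessment? | All patients with at least one dose (10.3) | All enrolled and dosed subjects (6.2, 17) |
| Who is in the vital-signs summary? | No age limit (10.5) | Aged 18 or over at consent (17.3) |
| Who may enrol? | Age 1 and over (4.3); children intended (synopsis) | Refers to the protocol criteria (4.1) |
| Is a change declared? | – | None (4.3) |
| Which document prevails? | – | The SAP (2) |

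The second row is a direct difference, and the fourth row says that no difference exists. The SAP modification history does not mention the restriction. Nor do the visible items of the later change form, which cover the effectiveness set definition, the adverse-event tables and the visit windows.

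**Step 2: patients affected**

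The number of children, k, is not given, so any value of k is an assumption. Share of the safety set left out = k/N, with N = 11 (SAP 4.1) or N = 10 (protocol 4.2), assuming all are dosed:

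| k (assumed) | k/11 | k/10 |
|---|---|---|
| 0 | 0% | 0% |
| 1 | 9.1% | 10% |
| 3 | 27.3% | 30% |
| 5 | 45.5% | 50% |

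The range runs from no loss at k = 0 to an empty table if every patient is a child.

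**Step 3: values affected per child**

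- Protocol 7.2.3 gives 4 measurements: systolic pressure, diastolic pressure, heart rate and temperature.
- Protocol Table 1 marks the row for vital signs, weight and height at Visits 1 to 12, which is 12 visits.
- 4 × 12 = 48 scheduled values at most. Adding weight, 48 + 12 = 60.
- Visit 1 precedes treatment, and Visit 2 procedures are done before the first dose. Post-dose vital-sign values are therefore 4 × 10 = 40.

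**Step 4: do other outputs fill the gap?**

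Physical examination has no age limit in SAP 17.2, but Table 1 schedules it only at Visits 1, 8, 10 and 12 (4 of 12 visits), and SAP 17.2 reports normal or abnormal by body system, not vital-sign values. Protocol 8.3.6 asks for deterioration in vital signs to be reported. That captures events, not the by-visit values that protocol 10.5 plans to summarize.

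**The case against.** **Adults and children should not be pooled.** Blood pressure, heart rate, height and BMI depend on age, and means taken from age 1 to adulthood in about 11 patients would be hard to interpret. This stands as a reason to present the groups separately. It is not a reason to omit one of them undeclared, and the SAP does not offer it.

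**Listings may cover children.** Protocol 10.5 and SAP 8.1 allow descriptive statistics and/or listings in general, SAP 9 leaves the outputs to a shell document, and part of the change form is not available. A pediatric listing, or a later correction, cannot be excluded. The finding is therefore about the SAP wording. That wording names no pediatric output, and the specific sentence in protocol 10.5 calls for descriptive statistics.

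**Weight is not a protocol vital sign.** This is correct. Protocol 7.2.3 leaves it out, and 10.4 and 10.5 promise no weight summary. Leaving children's weight untabulated is a practical loss but breaks no stated protocol analysis. The contradiction concerns blood pressure, heart rate and temperature.

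**The conflict with SAP 17 is soft.** Adults in the SAF are still a subset of the SAF, so section 17 can be read as naming the source population. The finding does not need this argument.

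**Consequences are small.** There is no hypothesis testing, and children remain in the adverse-event, laboratory, physical-examination, immunogenicity and effectiveness outputs. This limits the severity. It does not remove the contradiction.

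**Conclusion.** The concern holds. SAP 17.3 excludes patients under 18 at consent from a by-visit safety summary that the protocol plans for treated patients without an age limit, and SAP 4.3 says that nothing changed. The wording of SAP version 2.1 is clear on this.

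The practical size is uncertain. It depends on the unstated number of children and on shells and change-form content that cannot be seen. The 9.1% per child assumes that all 11 patients are dosed. The 48 values per child assume that every scheduled visit is attended, and 8 of them precede the first dose. No primary or secondary result is affected. The point should be corrected, but it does not threaten the study's main conclusions.

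**What to change.** In SAP 17.3, remove the adult-only restriction and present the listed measurements by visit for the whole SAF, with patients under 18 at consent shown separately from adults. Given the small numbers, a by-patient pediatric listing is an acceptable form.

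If the adult-only table is kept, state the restriction and its reason in SAP 4.3 and name the pediatric table or listing that covers the remaining patients. If the shells already contain such an output, a cross-reference in 17.3 plus the declaration in 4.3 would be enough.

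The change form already records additions dated 26 February 2025, after database lock, so this would be entered there as a documented post-lock change. The cost is a few lines of wording and one small table or listing from data already scheduled for collection. The drawback is few patients per age group, which is why a listing may be more useful than summary statistics for the children.

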8.3.6 Adverse Events Based on Examinations and Tests

The results from protocol-mandated laboratory tests and vital signs will be summarized in the clinical study report. Deterioration, as compared to baseline, in protocol-mandated laboratory values and vital signs should be reported as.

8.3.7 Any new or aggravated clinically significant abnormal medical finding at a physical examination as compared with the baseline assessment should also be reported. Hy's Law

Cases where a patient has an AST or ALT $\ge 3x$ ULN and total bilirubin $\ge 2x$ ULN may need to be reported as SAEs. Refer to Appendix B for further instruction in cases of combined increase of aminotransferase and total bilirubin.

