### 4.3 Changes to Analysis from Protocol

There are no changes to the analysis from the protocol.

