#### 6.2 Safety Analysis Set (SAF)

The safety analysis set (SAF) will contain all enrolled subjects who receive at least one documented dose of metreleptin and will be used in the assessment of safety.

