#### 17. SAFETY OUTCOMES

All outputs for safety outcomes will be based on the SAF.

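### SAP 17.3 limits the by-visit vital-sign summary to adults; the protocol sets no age limit and SAP 4.3 declares no change, so under-18s have no planned by-visit vital-sign or weight summary in the text available

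*SAP*

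**What the plan says.** Protocol 3.3 names vital signs over time among the safety outcome measures. Protocol 7.2.3 defines them: "Vital sign measurements will include sitting systolic and diastolic blood pressure and heart rate and body temperature". For the analysis, Protocol 10.5 says that "vital signs results will be summarized using descriptive statistics for each visit", with no restriction by age. Children are enrolled by design. The synopsis states: "Pediatric patients will be included since patients with congenital generalized lipodystrophy present with this condition at birth", and inclusion criterion 2 in Protocol 4.3 sets the minimum age at 1 year.

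SAP 17 opens with "All outputs for safety outcomes will be based on the SAF". SAP 6.2 defines that set as "all enrolled subjects who receive at least one documented dose of metreleptin", again without an age limit. SAP 17.3 then reads "Vital signs will be summarized among adult patients", with adulthood fixed as 18 years or more at informed consent. Its list covers height, weight, BMI, temperature, heart rate and blood pressure by visit. The only derivation, in SAP 17.3.1, is the BMI formula. SAP 4.3 states: "There are no changes to the analysis from the protocol".

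**The concern.** The age limit narrows a safety analysis that the protocol specifies for all treated patients, and the section meant to record such changes says there are none. SAP 2 lets the SAP override the protocol where the two differ, so the adult-only rule is the one a programmer would follow. A reader of the report who relied on Protocol 10.5 would expect children in the vital-sign table and would not be told that they had been taken out.

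The restriction falls on the group in which one of these measurements matters most. Protocol 9.2 and the synopsis both give excessive weight loss as an example of a reason to change the dose, and both single out children. Weight is measured at every visit, yet under-18s have no planned weight summary. For adults the plan gives raw weight at each visit, with no measure of how each patient changed.

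**Working it through.** The plan states no figure on this point, so there is nothing to reproduce. The check is a comparison of texts followed by simple arithmetic.

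**1. Who should be in the table.** Protocol 10.5 sets no age limit. SAP 17 and 6.2 point to all enrolled patients with a documented dose. SAP 17.2 (physical examination) and 17.4 (laboratory) apply no age limit either. Only 17.3 does. Because age is taken at consent, a patient who turns 18 during the 36 months stays out of the table throughout.

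**2. Whether children's data are summarised elsewhere.** SAP 11 (demographics) lists neither weight nor vital signs. SAP 17.2 records only normal, abnormal or not done. SAP 18 covers HbA1c, fasting glucose, triglycerides and leptin/metreleptin concentration. The three December 2024 changes that can be read in the SAP change form concern the effectiveness set, the adverse-event tables by antibody status and the visit windows. None adds a vital-sign or weight summary for under-18s.

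**3. Share of patients affected.** SAP 4.1 gives 11 patients; the number under 18 is not stated. With k under-18s, the share left out is k/11:
- k = 0: 0%
- k = 1: 1/11 = 9.1%
- k = 3: 3/11 = 27.3%
- k = 5: 5/11 = 45.5%, leaving 6 adults

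These values of k are assumptions. At k = 0 the restriction has no practical effect.

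**4. Why raw adult weights are a weak guide to weight loss (illustration, all weights assumed).** Six adults weigh 45, 50, 55, 60, 65 and 70 kg at baseline: mean 345/6 = 57.5, median 57.5, range 45 to 70. The 60 kg patient falls to 51 kg, which is −9/60 = −15%; the others do not change.
- *Everyone attends:* mean 336/6 = 56.0, median (51 + 55)/2 = 53, range still 45 to 70. The median drops by 4.5 kg, so the planned table does show something, though not that one patient lost 15%.
- *Two of the other five are absent (10 possible pairs):* if the absent pair weighs s kg in total, the raw mean changes by (336 − s)/4 − 57.5 = (106 − s)/4. This runs from +2.75 kg (s = 95) to −7.25 kg (s = 135) and is positive for 3 of the 10 pairs (s = 95, 100, 105).
- *Change from baseline in the four who attend:* mean −9/4 = −2.25 kg and minimum −15%, for every pair.

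**5. Why age at visit matters for a child (assumed values).** A fall from 20 to 18 kg by Month 12 is −2/20 = −10%. If 2 to 3 kg of growth was expected, the child is (22 − 18)/22 = 18.2% to (23 − 18)/23 = 21.7% below the expected weight.

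**The case against.** The strongest reply is that the restriction is sensible. Raw height, weight, heart rate and blood pressure pooled from toddlers to adults would be uninterpretable, and a separate table might rest on one or two children. The first part stands, but it supports separate presentation and a declared limit. It does not support leaving children out unannounced.

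Second, worsening in a child is not invisible. Protocol 8.3.6 calls for reporting of deterioration in vital signs against baseline (the sentence is incomplete in the text) and of "Any new or aggravated clinically significant abnormal medical finding at a physical examination". SAP 17.1 summarises adverse events without an age limit. Both documents allow listings in general terms, and SAP 9 refers to table shells that were not available. This also stands. A reader might infer that children's vital signs will go unreported altogether; the documents do not support that. None of these routes, however, is stated to be the by-visit summary that Protocol 10.5 specifies.

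Third, a reader might infer that the missing change from baseline in weight also breaches the protocol. It does not. Protocol 10.5 asks for no change from baseline in vital signs, 7.2.3 does not count weight among them, and weight loss is neither a named outcome nor an event of special interest. By tabulating weight and BMI at all, SAP 17.3 already goes beyond the protocol.

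**Conclusion.** The age limit in SAP 17.3 is an undeclared narrowing of the by-visit vital-sign summary in Protocol 10.5. In the text available, under-18s are left without a planned by-visit summary of vital signs or weight. The absence of within-patient weight change is a separate, smaller matter: a gap in both documents that is worth closing because the protocol itself links weight loss to dosing.

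The size cannot be determined. It depends on the number of under-18s, which is not given and may be zero, and the weight figures above are illustrations only. The conclusion is limited to the text available, since the table shells and part of the change form could not be read. The primary immunogenicity analysis is not touched. The point merits correction as a matter of safety reporting, with moderate confidence.

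**What to change.** 1. In SAP 17.3, present vital signs and weight for patients under 18 at consent separately by visit. If numbers are small, use a per-patient listing with age at visit and change from baseline.
2. In SAP 4.3, declare that the pooled vital-sign table is restricted to adults, and give the reason.
3. As an improvement, add absolute and percentage change from baseline in weight at each visit for adults, as SAP 18.2 already does for the exploratory variables.
4. Weight-for-age z-scores for children are optional. They need a named growth reference, and one drawn from the general population may fit lipodystrophy imperfectly.

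The cost is a few lines of SAP text, one derivation and one table or listing. Weight and the other measurements are already collected, and date of birth is already used to derive age in SAP 11.1. If BMI change is added, limit it to visits with a measured height: Table 1 of the protocol marks height at every visit, whereas Protocol 6.3 ties it to Visits 8, 10 and 12. The change form already records changes dated February 2025, after database lock, so anything added now should be labelled post hoc.
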